In terms of needed time to recruit our targeted patient population, based on our data from our recently completed research study (mentioned above) at 19 Kroger sites and based on our previous screening study and small scale study, we expect to approach 9 patients for recruitment monthly at each of our pharmacy locations.  With this rate and based on our procedure mentioned above of 1:1 recruitment of individuals with risk/non-risk alcohol use, study recruitment will require approximately 13-months to complete. We have chosen to focus recruitment at a limited number of sites (N=3) during feasibility/acceptability/preliminary efficacy testing to ensure internal validity of our procedures, limiting possible site variation, and limiting multisite challenges. During screening, we will capture sex, insurance status, and age for all eligible patients to assess basic demographic differences among those who participate versus those that do not.

While definitive estimation and hypothesis testing are not the aim of this study, the target sample size will allow estimation of odds ratios via 95% confidence intervals comparing outcome rates in the intervention and control arms, while accounting for within site clustering, with lower bounds differing from the odds ratio estimate by a factor of 1/3 to 1/2 and upper bounds differing from the odds ratio estimate by a factor of 2 to 3 for a broad range of overall rates, true odds ratios, and magnitude of site-to-site effects. In particular, this study will allow detection of strong signals of preliminary benefit and provide suggestions of benefit for more subtle signals.

- Element 4 is the intervention and/or referral. This is where the pharmacist would employ SBIRT to work with the participant to either choose (1) to eliminate alcohol use during opioid therapy OR (2) to facilitate communication with the prescriber to select a non-opioid pain management alternative. SBIRT is an evidence-based practice for improving alcohol problems,  with demonstrated evidence from pharmacists and other providers for medication adherence improvement and reductions in problematic prescription opioid use.  It is highly important to note that in the current application context, SBIRT targeting elimination of co-use of alcohol and opioids (i.e., alcohol use elimination during opioid treatment OR non-opioid pain management substitution) is designed to prevent related sequelae, i.e., possible overdose risk and use disorders. We do recognize, however, some participants may not choose the non-opioid pain treatment option and also be ambivalent about elimination of alcohol use. These participants will be encouraged to reduce alcohol use.
- Element 5 includes documentation and follow up. Documentation includes the pharmacist recording notes/action items related to elements 1-4. The follow-up (booster session) portion includes scheduling a telephonic session 7 days following the initial visit, during which the pharmacist reviews commitments made during the initial session, works to resolve barriers, and provides additional referrals/resources.

**SA2 assessment, follow up, and retention.** Participants will be assessed at baseline, 2-months, and 3-months post-randomization at the Kroger community pharmacy settings or other appropriate locations. Participants will be compensated \$40 for the baseline assessment, \$50 for the 2-month, and \$75 for the 3-month—with a \$75 completion bonus for those completing all assessments. Research assistants will aid participants to complete self-administered portions of the questionnaires as necessary to prevent missing data and ensure accurate/completed assessments. Research assistants will also be trained to administer urine toxicology assessments to participants. Efforts to ensure continued participant contact include collecting locator information and at least 2 collateral contacts as well as sending letters and cards, electronic messages, and making phone

calls. Noted above, these retention methods were successful in the BI-MTM study, resulting in >93% retention at the final study follow up. 102

SA2 intervention feasibility and acceptability outcome measurement. Achievement of feasibility of delivery of all intervention components to 85% of ABI-MTM recipients will be captured by the pharmacist logging completed intervention components. Achievement of ABI-MTM acceptability will be assessed at month 3 and will be captured by intensive qualitative interview following a semi-structured interview guide focusing on participant opinions/experience with ABI-MTM. Acceptability will also be captured at month 3 by assessing patient satisfaction using the Patient Satisfaction Survey for Comprehensive Medication Management (PSSCMM), a reliable and content/factorially valid 10-item self-report instrument that will assess patient satisfaction with intervention. Last, acceptability will also be assessed by intervention recipient retention (85%) at study completion.

SA2 preliminary efficacy outcome measurement. This aim postulates that intent-to-treat analyses will show greater proportions of ABI-MTM recipients will report elimination of co-use of alcohol and opioid medications compared to SMC. 35,36 Our primary assessments will include:

- Timeline Follow Back (TLFB) assesses quantity/frequency of alcohol and opioid medication use, which is a measure that is reliable and is content, criterion, and construct valid. 35,36 Also note, we will capture any illicit drug use with the TLFB.
- 14 panel drug urinalysis will be collected in private restrooms of the pharmacies or other appropriate locations, which will capture opiates, oxycodone, methadone, cannabis, cocaine, PCP, amphetamine, MDMA, methamphetamine, barbiturates, benzodiazepines, buprenorphine, tricyclic antidepressants, and propoxyphene. Participants are considered co-use free if self-report and urine assessments coincide.

In addition to our primary outcome measures, we will also capture concomitant conditions as covariates at each time point. Each of these conditions are well known correlates of opioid related risk, substance use, and health behavior change:

# Opioid Use Behaviors 122,123

- Prescription Opioid Misuse Index (POMI), a 6-item criterion valid and reliable measure that assesses prescription opioid misuse behaviors and opioid medication misuse. 124
- Opioid Compliance Checklist (OCC), an 8-item, a test/retest reliable and criterion valid tool 125-127 that assesses adherence/misuse to the prescribed opioid regimen.
- Diagnostic Statistical Manual-5 Checklist for Opioid Use Disorder, is an 11-item reliable and valid assessment that identifies mild, moderate, and severe opioid use disorder. 128,129 Pain and Physical Health 130-133

- Brief Pain Inventory, is a well-validated and reliable assessment, which consists of a 4-item pain intensity subscale and a 7-item pain interference subscale. 134
- Pain Catastrophizing Scale, a 13-item factorially/concurrent/discriminant valid and reliable assessment that measures rumination, magnification, and helplessness aspects of pain catastrophizing.
- Short Form-36 (SF-36) will assess physical health and is a 36-item content, criterion, and construct valid measure with demonstrated reliability. 136 This measure assesses physical functioning, role functioning, bodily pain, general health, vitality, social functioning, emotional functioning, and mental health.

# Mental Health and Risk Alcohol Use

- Patient Health Questionnaire (PHQ) will assess mental health and is an 11-item criterion valid mental health assessment with demonstrated reliability. 137-140 The PHQ assesses depression, anxiety, somatoform, eating, and alcohol use disorders. This assessment will also be used to monitor suicidal ideation across time.
- Primary Care-Posttraumatic Stress Disorder assessment will measure post-traumatic stress disorder, which is a 5-item criterion valid and test-retest reliable instrument. 141-144
- Alcohol Use Disorders Identification Test-C (AUDIT-C) is a 3-tem abbreviated version of the AUDIT-10, which has demonstrated internal consistency and test-retest reliability and construct and criterion validity. 37,92 The AUDIT-C has highly similar performance as the full version and assesses frequency, quantity, and binge drinking (note, the AUDIT-C will be administered at screening [not baseline], 2-, and 3-months assessments).
- WHO Alcohol, Smoking, and Substance Involvement Screening Test alcohol subscale will be used to assess lifetime and recent alcohol use. This 7-item measure has demonstrated reliability as well as criterion, construct, concurrent, discriminant validity. 145

# Engagement in Physical Health and Psychosocial Services

Treatment Services Review (TSR)-6 will assess engagement in services for: substance abuse, medical/mental health, family issues, financial/housing needs, and legal concerns. The TSR-6 also captures medication use; which we will use to capture type, dose, and frequency of opioid consumption and other medications. The TSR contains 56-items and is criterion and construct valid and reliable. 146-149 The TSR will be used, in particular, to identify length of the written opioid prescription, which will allow for examination of elimination of co-use during the opioid treatment. This will also allow for monitoring of natural cessation of opioid use during the course of treatment

# Readiness to Change 150,151

The Readiness to Change Questionnaire is a 12-item assessment of individual readiness to change drinking behaviors that evaluates three of the stages of change: pre-contemplation, contemplation, and action. This assessment has content, criterion, and construct validity—with test-retest reliability. 152-155

Social Desirability

The Marlowe-Crowne Social Desirability Scale and short Form contains 13 items and is criterion valid and reliable. This measure will assess the participants' degree of social desirability at each time point.

**SA2** acceptability and feasibility analysis plan. Successful delivery of all intervention components will be analyzed by calculating the total number recipients that received both ABI-MTM sessions divided by the total number of participants randomized to this condition. Intensive qualitative interviews of ABI-MTM acceptability will be analyzed following methods recommended by Braun and Clarke that capture associations between categories, extract, and conceptualize themes. Our team will independently review the interview data and code inductively and deductively. Codes will be clustered based on their similarities into categories. The research team will meet multiple times to discuss the emergent themes. Patient satisfaction with the intervention reported on the PSSCMM will be analyzed by calculating frequencies of responses, measures of central tendency, and proportions. Treatment retention of 85% of ABI-MTM recipients at study completion will be analyzed by calculating number of recipients retained at 3-months divided by number of consented recipients.

**SA2** preliminary efficacy analysis plan. This aim compares the preliminary efficacy of the intervention (ABI-MTM vs. SMC) on the primary binary co-use outcome (i.e., co-use vs. no co-use of alcohol and opioid medications). Mentioned above, successful elimination of co-use can be in the form of (1) participants eliminating their alcohol consumption while they are receiving opioid therapy, which will be measured by the TLFB, OR (2) by choosing an alternative non-opioid pain management strategy (not altering their alcohol consumption) by recommendation of the pharmacist and in collaboration with their prescriber, which will be measured by agreement of urine toxicology and TLFB.

We will first provide descriptive summaries of each variable measured at baseline, 2-, and 3-months overall, by risk/non-risk alcohol use, as well as by intervention group (note that all included participants are positive for co-use at baseline). Within an intent-to-treat framework, we will fit 3-level generalized linear mixed models (GLMM) to relate repeated assessments across time of the primary outcome measured (i.e. elimination of co-use) to the intervention. Additional analyses within the 3-level GLMM framework will also be conducted to assess the overall impact of the intervention on reducing percent days alcohol use among patients during the prescribed opioid treatment period. All analyses will be adjusted for covariates likely to be associated with the outcome. Specifically, this will include baseline measures such as opioid use, mental health, substance use, pain/physical function, social services utilization, and readiness to change in addition to and demographic covariates including (but not be limited to) age, sex, race, socioeconomic status, and rural/urban living. 159 Social desirability will also be included as a time varying covariate to account for the degree to which participant response bias may impact study outcomes. Random intercepts will be used to account for correlations on the patient level and pharmacy site level. We will also test risk/non-risk alcohol use as an effect modifier to determine whether the intervention has a differential impact on individuals with distinct levels of drinking; we recognize, however, the sample study sample size may limit the power of the analysis to detect changes at a probability of <0.05. Thus, it is important to note our above discussed analysis focus on 95% confidence intervals comparing outcome rates in the intervention and control arms in order to detect subtle trends in relation to intervention efficacy. Model parameters, including treatment effects at each follow-up, will be estimated using restricted maximum likelihood. 160 An advantage of this approach is treatment effect estimates remain consistent and approximately unbiased if missing data follow a missing-at-random pattern (MAR; data values are independent of the missingness mechanism conditional on the observed data), the most general data-centric missing data assumption.

As biological sex is an important factor among individuals with pain and opioid/alcohol use,  we will explore differences by intervention group and biological sex for SA2. Based on our previously published research in this population, we anticipate recruiting ~57% females/~43% males in this study. We will first examine descriptive demographic differences at baseline, 2-, and 3-months within the ABI-MTM and SMC conditions by sex. Next, to explore the potential role of sex as an effect modifier for ABI-MTM on co-use, we will test interaction terms between the intervention group and sex to explore possible heterogeneity of treatment effects and to characterize if sex subgroups might benefit more from the intervention. As discussed above with reference to the risk/non-risk alcohol use as an effect modifier analyses, sex subgroup analyses will likewise focus on 95% confidence intervals comparing outcome rates in the intervention and control arms in order to detect subtle trends in relation to intervention efficacy.

**SA2 product.** By successfully accomplishing SA2, this will establish the necessary feasibility, acceptability, and preliminary efficacy data to demonstrate ABI-MTM is ready for a subsequent fully powered multisite randomized trial.

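### The co-use model adjusts for at least 12 covariates in 40 people with no short primary model, and the stated precision (factor 2 to 3) fails at each follow-up and over a broad range of rates

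*Combined protocol and SAP*

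**What the plan says.** The model is described under SA2 preliminary efficacy analysis plan. A three-level generalized linear mixed model relates co-use at follow-up to arm, with random intercepts for patient and site. On adjustment: "All analyses will be adjusted for covariates likely to be associated with the outcome". The list covers "baseline measures such as opioid use, mental health, substance use, pain/physical function, social services utilization, and readiness to change" and "demographic covariates including (but not be limited to) age, sex, race, socioeconomic status, and rural/urban living". Social desirability "will also be included as a time varying covariate to account for the degree to which participant response bias may impact study outcomes". The same framework serves a second outcome, "reducing percent days alcohol use among patients during the prescribed opioid treatment period". On estimation: "Model parameters, including treatment effects at each follow-up, will be estimated using restricted maximum likelihood".

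The section notes that every participant is co-use positive at baseline. It makes 95% confidence intervals the basis for reading the result and concedes limited power for the test of risk drinking as an effect modifier. It gives no reduced model, covariate selection rule, penalty or fallback.

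The precision forecast is under SA2 recruitment feasibility, randomization, sample size, and justification. It opens with "While definitive estimation and hypothesis testing are not the aim of this study" and then expects "upper bounds differing from the odds ratio estimate by a factor of 2 to 3 for a broad range of overall rates", with the lower limit at a third to a half of the estimate. It allows for clustering within site. It names no visit and no covariates.

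**The concern.** The co-use outcome is constant at baseline, so all outcome information comes from months 2 and 3 in 40 people. Twelve or more fixed effects, plus arm and visit, is a heavy load for that amount of binary data. In a logistic model it widens the interval, pushes the odds ratio away from 1 and raises the chance of separation or non-convergence. The precision forecast mentions clustering but not this load, and the plan wants an effect at each visit.

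The next trial's planners will use the estimate and its interval. An exaggerated odds ratio, with an interval wider than the protocol led them to expect, is a poor basis for that step. Two smaller gaps sit beside this. Restricted maximum likelihood does not by itself identify an estimator for binary data. And the risk-drinking randomisation stratum appears in the analysis only as an effect modifier.

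**Working it through.** **Inputs from the documents.** 40 randomised, 20 per arm; two follow-up visits; 95% intervals; 85% retention target. That target is stated for the intervention arm. Applying it to both arms, which gives 0.85 × 20 = 17 per arm, is an assumption. The documents give no outcome rates or within-person correlation, so ranges are used.

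**Covariate count.** 6 + 5 + 1 = 12 if each enters as one term. Both lists are open-ended, so this is a minimum. With arm added there are 13 parameters. At one visit, events per parameter are 20/13 = 1.5, 12/13 = 0.9 and 8/13 = 0.6 at rates of 50%, 30% and 20%.

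**What the stated factor requires.** The factor is exp(1.96 × SE of the log odds ratio). A factor of 3 needs variance (ln 3/1.96)² = 0.314. A factor of 2 needs (ln 2/1.96)² = 0.125. At one visit with both rates 50%, the variance is 2/(n × 0.25) = 8/n. So factor 3 needs 8/0.314, or 26 per arm, and factor 2 needs 8/0.125 = 64 per arm.

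**One visit, unadjusted.** Variance = 1/(n·p1·q1) + 1/(n·p2·q2). With n = 20 and both rates 50% it is 0.40, and exp(1.96 × 0.632) = 3.45. This is the Wald floor, because pq cannot exceed 0.25. A score interval gives 3.39 and profile likelihood 3.49. Only a 90% interval falls below 3 (2.83), and the plan says 95%.

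**Both visits pooled, unadjusted.** Multiply the variance by (1 + r)/2, where r is the within-person correlation. A factor of 3 then needs r ≤ 2 × 0.314/variance − 1.

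| Rate (equal arms) | One visit, n = 20 | One visit, n = 17 | Pooled, r = 0 | Pooled, r = 0.5 | Largest r for factor 3 | Same, true OR 3 at that control rate |
|---|---|---|---|---|---|---|
| 50% | 3.45 | 3.84 | 2.40 | 2.93 | 0.57 | 0.35 |
| 30% | 3.87 | 4.34 | 2.60 | 3.23 | 0.32 | 0.42 |
| 20% | 4.71 | 5.37 | 2.99 | 3.83 | 0.01 | 0.22 |

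The pooled columns and the last two columns use n = 20. Example for the last column: control 20% and OR 3 give an intervention rate of 0.75/1.75 = 43%, variance 0.517, and r ≤ 0.628/0.517 − 1 = 0.22. With non-negative correlation the best pooled factor is 2.40, so 2 is never reached. These pooled figures are marginal; an odds ratio conditional on a patient intercept would have a wider factor.

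**Effect of 12 covariates (simulation, assumption-dependent).** The settings were N = 40, both visits complete, true OR 1 or 3 and 500 trials per setting. Patient SD was 0.5 to 1.5, site SD 0.3 to 0.5, and prognostic scores carried 0.2 to 0.4 log odds per SD. The comparison is with a short model (stratum, site, one baseline score).

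- Pooled factor at control rates of 30–50%, pseudo-likelihood: 4.9–11.9 against 3.0–4.3, or 1.6–2.8 times wider.
- The same, maximum likelihood: 3.8–7.4 against 2.9–6.4, or 1.1–1.4 times wider.
- True OR 3: the 12-covariate median was 3.7–4.6, with 18–29% of estimates above 10 or below 0.1. Under the short model that share was 3–5% (pseudo-likelihood) or 8–17% (maximum likelihood).

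A separate ordinary logistic check used covariates with no effect and treated the visits as independent, which flatters precision. With 12 covariates it gave pooled factors of 3.3, 3.8 and 5.1 at 50%, 30% and 20%, against 2.4, 2.6 and 3.1 with none. None of these figures apply to the percent-days outcome.

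**The case against.** The forecast is tied to no visit, and the model uses repeated assessments. Pooled and unadjusted, a factor within 3 is attainable at rates of 30–50% with low to moderate correlation. This stands: a reader might infer that the stated precision is unreachable under any analysis, and the documents do not support that. The correlation limits also depend on the true effect; the near-impossibility at 20% belongs to equal rates.

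Much of the gap comes from having 40 people. A short model will not guarantee a factor of 3 either, so a reader should not infer that covariates are the whole cause. The penalty also depends on the estimator: under maximum likelihood the long-model and short-model ranges overlap heavily.

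Nor are the intervals invalid. Simulated coverage with 12 covariates was 90.6–94.3% (maximum likelihood) and 93.4–99.0% (pseudo-likelihood).

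The plan cites a methods paper whose title says that adjustment for dichotomous outcomes raises power. That favours adjusting for a few strong predictors. It does not imply a narrower odds ratio interval, because in a logistic model the estimate and its standard error can both grow. It also does not address 12 terms in 40 people.

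This is a pilot, its size is not power-based, and descriptive summaries by arm are planned. That limits the harm, but such summaries are not an odds ratio with an interval, and the plan rests its reading on intervals.

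It is tempting to say that adjusting for social desirability at follow-up biases the intent-to-treat contrast. It is measured after randomisation, so it could alter that contrast. But nothing in the documents sizes the effect, and contacts are matched between arms (SA2 treatment-as-usual and intervention conditions).

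**Conclusion.** The point holds. At each planned follow-up, the stated factor of 2 to 3 is not met even without covariates, clustering or dropout: 3.45 at best, 4.71 at rates of 20%, and 3.84 at best with 17 per arm. Pooled, it holds only for part of the range claimed, and its lower end of 2 is out of reach. These results are closed-form, for Wald intervals. Assumed rates enter the individual figures but not the 3.45 floor.

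A 12-covariate model with no short primary model makes precision worse and exaggerates the odds ratio. The direction was consistent across the checks. The size, about 1.1 to 2.8 times wider at control rates of 30–50%, rests on the estimator and on assumed effects. This should be corrected before analysis; it does not undermine the trial's feasibility and acceptability aims.

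**What to change.** In the SAP, make the primary co-use model short: arm, visit, arm-by-visit, risk-drinking stratum, one named baseline Timeline Follow-Back alcohol measure with its window, and site and patient terms. State whether the primary effect is pooled over both visits or at month 3. Name the binary-data estimator, and a fallback for separation or non-convergence to be reported if used. In simulation even a short model failed to fit in up to 6% of trials at a 20% control rate. Move the remaining covariates, one named score per domain, to labelled sensitivity models, with time-varying social desirability labelled as a response-bias analysis. Whether site is fixed or random, and the form of any penalty, are choices for the sponsor.

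Restate the precision with its assumptions: unadjusted, 20 per arm, equal rates of 50% to 20%, a factor of about 3.5 to 4.7 at one visit and about 2.4 to 3.8 pooled for within-person correlation of 0 to 0.5. Say that covariates, site variation or loss to follow-up widen it.

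The cost is wording only, since the plan already collects these variables. The downsides are less adjustment for chance imbalance, response bias handled only in sensitivity analysis, and an odds ratio pulled somewhat toward 1 by leaving out prognostic factors (short-model median 2.4–3.3 for a true 3 in the simulation).

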
**SA1:** Adapt/manualize an *Alcohol-targeted* Brief Intervention-Medication Therapy Management intervention. *Rationale*: BI-MTM was developed to address opioid medication misuse and comorbid health conditions (e.g., pain, mental health); yet, it was not designed for universal delivery to patients with active opioid prescriptions and concurrent alcohol use. *Approach*: We will utilize the ADAPT-ITT (Assessment, Decision, Administration, Production, Topical Experts, Integration, Training, and Testing) framework to modify/manualize BI-MTM for delivery to community pharmacy patients with co-use of alcohol (both risk level and non-risk level alcohol use) and opioid medications (i.e., an *Alcohol-targeted* Brief Intervention-Medication Therapy Management or *ABI-MTM*). *Outcome*: Completion of SA1 will result in a manualized protocol for clinical trial evaluation.

SA2: Test the Feasibility, Acceptability, and Preliminary Efficacy of ABI-MTM for Community Pharmacy Patients with Concomitant Alcohol and Opioid Medication Use. Rationale: The extent to which ABI-MTM: is acceptable to patients, can be feasibly delivered in community pharmacy settings, and can mitigate couse of alcohol and opioid medications is unknown. *Approach*: We will conduct a small-scale trial in 3 community pharmacies and enroll those with/without risk drinking, with a stratified randomization to ABI-MTM (1:1 ratio; risk use n=10; non-risk use n=10) or standard medication counseling (SMC; risk use n=10; non-risk use n=10). *Outcome 1*: Feasibility will be established through delivery of both ABI-MTM components to 85% of ABI-MTM recipients. *Outcome 2*: Acceptability will be demonstrated through qualitative interviews, patient satisfaction, 33,34 and participant retention (85%) at study completion. *Outcome 3*: Intent-to-treat analyses will show greater proportions of ABI-MTM recipients will eliminate co-use of alcohol (risk and non-risk alcohol use) and opioid medications compared to SMC assessed by Timeline Follow-Back and urine toxicology. 35-37 *Product*: Accomplishing SA2 demonstrates ABI-MTM is positioned for a subsequent fully-powered multisite randomized trial.

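### With about 10 patients per cell, 95% confidence intervals cannot reveal subtle differences in effect by risk drinking or sex, as the plan says they will

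*Combined protocol and SAP*

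**What the plan says.** The trial randomises 40 patients: "1:1 ratio; risk use n=10; non-risk use n=10) or standard medication counseling (SMC; risk use n=10; non-risk use n=10" (Specific Aims, SA2).

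The SA2 preliminary efficacy analysis plan then sets out two effect-modifier analyses.

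- **Risk drinking.** "We will also test risk/non-risk alcohol use as an effect modifier", with the purpose "to determine whether the intervention has a differential impact on individuals with distinct levels of drinking". The same sentence accepts that the sample may limit power at the 0.05 level. The next sentence draws a consequence from that: the plan will "focus on 95% confidence intervals comparing outcome rates in the intervention and control arms in order to detect subtle trends in relation to intervention efficacy".
- **Sex.** "we will test interaction terms between the intervention group and sex to explore possible heterogeneity of treatment effects". The second stated purpose of this analysis is "to characterize if sex subgroups might benefit more from the intervention". The paragraph refers back to the risk-drinking analyses and says that "sex subgroup analyses will likewise focus on 95% confidence intervals comparing outcome rates in the intervention and control arms in order to detect subtle trends".

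The only precision figure is in the SA2 section on recruitment feasibility, randomization and sample size. It covers the overall arm comparison, with 95% limits a factor of 2 to 3 above the odds ratio estimate and 1/3 to 1/2 below it. No width is given for any subgroup or interaction estimate.

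**The concern.** The plan admits that the subgroup tests may be underpowered and offers confidence intervals as the way round it. They are not. A 95% Wald interval and a two-sided 5% Wald test are built from the same estimate and standard error, so the interval excludes no effect exactly when the test is significant. Reporting intervals is better practice because they show how little is known, but they add no sensitivity to small differences.

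What is at stake is interpretation. With about 10 patients per cell, sizeable differences between subgroups will often arise by chance. A plan that says its intervals pick up subtle trends invites those differences to be reported as signals, and the Conclusion says that the results will inform a powered multisite trial.

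**Working it through.** **Inputs from the documents**
- 10 patients per cell by arm and risk drinking, so 20 per arm.
- Sex: "we anticipate recruiting ~57% females/~43% males". Per arm this is 0.57 × 20 = 11.4 women and 0.43 × 20 = 8.6 men, if sex splits evenly between arms.
- 95% two-sided intervals, so z = 1.96.
- Two informative visits, at 2 and 3 months. Everyone is co-use positive at baseline, so baseline adds no information on the binary outcome.

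**Assumptions (not in the documents)**
- Elimination rate p of 30% to 50%, the same in all cells.
- Either one visit, or two pooled visits with within-patient correlation ρ = 0.5.
- Wider check: p from 20% to 50%, and ρ from 0 up to the single-visit case.

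**Formulas.** V = sum over cells of 1/[n p (1 − p)]. For two pooled visits, multiply V by (1 + ρ)/2, which is 0.75 at ρ = 0.5. The limits lie a factor F = exp(1.96 √V) either side of the estimate.

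**1. The plan's own figure (20 versus 20)**
- p = 50%: V = 2/(20 × 0.25) = 0.400, F = 3.45. Two visits: V = 0.300, F = 2.93.
- p = 30%: V = 2/(20 × 0.21) = 0.476, F = 3.87. Two visits: V = 0.357, F = 3.23.
- Two visits with ρ = 0: F = 2.40 (p = 50%) to 2.99 (p = 20%).

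The stated 2 to 3 is therefore met only with two pooled visits and favourable rates or correlation. The lower figure, 2, is not reached in any case computed.

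**2. Arm comparison within a risk-drinking subgroup (10 versus 10), and 3. interaction (four cells of 10)**

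| | V, within | F, within | V, interaction | F, interaction |
|---|---|---|---|---|
| p = 50%, one visit | 2/(10 × 0.25) = 0.800 | 5.8 | 4/(10 × 0.25) = 1.600 | 11.9 |
| p = 50%, two visits | 0.600 | 4.6 | 1.200 | 8.6 |
| p = 30%, one visit | 2/(10 × 0.21) = 0.952 | 6.8 | 4/(10 × 0.21) = 1.905 | 15.0 |
| p = 30%, two visits | 0.714 | 5.2 | 1.429 | 10.4 |

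Taking p as the control rate, with a true odds ratio of 2 or 3 in each subgroup, leaves every result inside these ranges. Over the wider assumptions at 10 per cell, the interaction factor runs from 5.8 (p = 50%, two visits, ρ = 0) to 22 (p = 20%, one visit). If 85% are retained (8.5 per cell) and p is 30–50%, it is 14.7 to 18.8 for one visit and 10.3 to 12.7 for two.

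**4. Sex.** At p = 50% and one visit, the interaction has V = 2/(11.4 × 0.25) + 2/(8.6 × 0.25) = 0.702 + 0.930 = 1.632, so F = 12.2. Over the main assumptions the interaction runs from 8.7 to 15.4. One-visit arm comparisons run from 5.2 to 6.0 in women and 6.6 to 7.9 in men.

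**5. From the plan's own precision.** Halving each arm doubles V, so a within-subgroup factor is the overall factor to the power √2: 2^1.414 = 2.7 and 3^1.414 = 4.7. The interaction has four times the variance, so its factor is the square: 2² = 4 and 3² = 9. This step needs no assumed rate.

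**6. Power of the interaction.** Power = Φ(ln R/SE − 1.96) + Φ(−ln R/SE − 1.96). At p = 50%, SE = √1.600 = 1.265 for one visit and √1.200 = 1.095 for two. A true ratio of odds ratios R = 2 gives 8.5% and 9.7%. R = 3 gives 14% and 17%.

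**7. Chance patterns.** Suppose all four cells share one true rate and there is one visit. The difference between the two subgroups' arm differences, counted in tenths, has SD √(4 × 10 × 0.25) = 3.16 at p = 50%. A gap of 30 percentage points or more then has probability about 2[1 − Φ(2.5/3.16)] = 43%. At p = 30% the SD is 2.90 and the probability is 39%.

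Site clustering and the planned covariates are left out. With conditional odds ratios in about 40 patients, the covariates would be expected to widen these intervals.

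**The case against.** **The plan is modest elsewhere.** It does not base sample size on power, disclaims definitive testing, concedes limited power for the modifier analysis, and writes about sex in exploratory terms. Stressing intervals over p-values is ordinary good practice in a pilot. All of this stands. It limits the point to a few words, and the phrase "to characterize if sex subgroups might benefit more from the intervention" needs no change.

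**The sentences describe arm comparisons, not interactions.** This also stands. A reader might take 9 to 15 as the width of the intervals the plan describes. It is not: the text names intervals comparing arms, so 4.6 to 6.8 is the primary figure and the interaction is a separate quantity. One could go further and say that the risk-drinking sentence refers only to the overall comparison. The sex paragraph rules that out, because it ties the interval focus to the risk-drinking modifier analyses and extends it to the sex subgroups.

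**The widths rest on assumed rates and correlation.** They do, and 9 to 15 is a middle band within 5.8 to 22. The conclusion survives because the plan's own figures give 4 to 9.

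**Stronger readings that do not hold**
- A reader might infer that the next trial would be restricted to one subgroup. No passage says so. The protocol argues that no level of co-use is safe and defends enrolling non-risk drinkers.
- A reader might infer that the interaction terms are useless and should go. Very large differences remain detectable: for 80% power, exp[(1.96 + 0.84) × SE] is about 21 at SE 1.095 and 48 at SE 1.380 (√1.905). Such ratios are extreme, but the terms are prespecified and harmless if labelled exploratory.
- A reader might extend these widths to percent days of alcohol use. That outcome is not binary, and the calculation does not describe its precision.

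**Conclusion.** The point holds as a correction to a stated capability. On the binary co-use outcome, the plan's intervals will not reveal subtle differences by risk drinking or sex, and presenting them in place of a test does not change that. Under the stated assumptions, within-subgroup limits for risk drinking lie about 4.6 to 6.8 either side of the odds ratio, and interaction limits for either modifier about 9 to 15 either side. The exact widths are conditional, but the direction of the conclusion is not. The design, the primary comparison and the decision to explore both modifiers are unaffected.

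**What to change.** In the SA2 preliminary efficacy analysis plan:

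1. In the risk-drinking sentence, change *determine whether* to *explore whether*.
2. For the risk-drinking and sex analyses, delete the clause giving detection of subtle trends as the purpose of the intervals.
3. State the expected widths with their assumptions. For example: assuming 30–50% elimination, and one visit or two pooled visits with correlation 0.5, 95% limits are expected to lie a factor of about 4.6 to 6.8 either side of the odds ratio within a risk-drinking subgroup, and about 9 to 15 either side of the ratio of odds ratios for an interaction. Add that these widths apply to the binary co-use outcome.
4. Keep the exploratory interaction terms. Also report the number eliminating co-use out of the number assessed, per arm within each subgroup, with exact 95% intervals. Label these results descriptive and not sufficient evidence of a differential effect.

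The cost is small: a stated capability becomes less favourable, and there is a little extra tabulation. No data collection, sample size or model changes.
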